5.2 Trial Treatment

The treatment to be used in this trial is outlined below in Table 5.

Table 5. Trial Treatment

Drug	Dose/Potency	Dose Frequency	Route of Administration	Regimen/Treatment Period
L-NMMA	15.0 mg/kg (starting dose)	Q3W	IV infusion	Days 1–5 of each 3-week cycle
Pembrolizumab	200 mg	Q3W	IV infusion	Day 5 of each 3-week cycle
Q3W = every 3 weeks; IV = intravenous				

L-NMMA and pembrolizumab will be administered for 6 cycles. Cycle length will be 21 days. L-NMMA will be administered as a 2-hour intravenous (IV) infusion on Days 1–5 at each cycle. The dose levels of L-NMMA are as follows: Dose Level -1, 12.5 mg/kg; Dose Level 0 (starting dose), 15.0 mg/kg; and Dose Level 1, 20.0 mg/kg. L-NMMA dose will escalate/de-escalate based on the occurrence of DLTs (see Section 8.0 — Statistical Considerations). Pembrolizumab at a fixed dose of 200 mg will be IV infused over 30 minutes on Day 5 at each cycle. Pembrolizumab will be administered 1 hour (\pm 10 minutes) after L-NMMA infusion on Day 5 at each cycle. Subjects will receive the trial treatment past 3 weeks only if they have tolerated the trial treatment without a DLT and their disease has not progressed. Subjects without disease progression after 6 cycles of L-NMMA and pembrolizumab will continue pembrolizumab until disease progression or unacceptable AEs. Subjects will be followed for a maximum of 3 months after the final treatment dose.

5.2.1 Dose Selection/Modification

5.2.1.1 Dose Selection

The rationale for the selection of doses to be used in this trial is provided in Section 1.2.2 — Rationale for Dose Selection.

5.2.1.2 Dose Modification

Pembrolizumab:

AEs (both non-serious and serious) associated with pembrolizumab exposure may represent an immunologic etiology. These AEs may occur shortly after the first dose or several months after the last treatment dose.

Withhold pembrolizumab for any of the following:

- Grade 2 pneumonitis

- Grade 2 or 3 colitis
- Grade 3 or 4 endocrinopathies
- Grade 4 hematological toxicity in subjects with cHL
- Grade 2 nephritis
- AST or ALT > 3 and up to 5 X ULN or total bilirubin > 1.5 and up to 3 X ULN
- Any other severe or Grade 3 treatment-related AE

Resume pembrolizumab in subjects whose AEs recover to Grade 0–1.

Permanently discontinue pembrolizumab for any of the following:

- Any life-threatening AE (excluding endocrinopathies controlled with hormone replacement therapy or hematological toxicity in subjects with cHL)
- Grade 3 or 4 pneumonitis or recurrent pneumonitis of Grade 2 severity
- Grade 3 or 4 nephritis
- AST or ALT > 5 X ULN or total bilirubin > 3 X ULN
 - For subjects with liver metastasis who begin treatment with Grade 2 ALT or AST, if ALT or AST increases by $\geq 50\%$ relative to baseline and lasts for at least 1 week
- Grade 3 or 4 infusion-related reactions
- Inability to reduce corticosteroid dose to 10 mg or less of prednisone or equivalent per day within 12 weeks
- Persistent Grade 2 or 3 AEs (excluding endocrinopathies controlled with hormone replacement therapy) that do not recover to Grade 0–1 within 12 weeks after the last dose of pembrolizumab
- Any severe or Grade 3 treatment-related AE that recurs

L-NMMA:

Blood pressure will be monitored during L-NMMA infusions. At each L-NMMA infusion, blood pressure will be measured before infusion, 1 hour (± 15 minutes) after infusion start, and at infusion completion. Automatic blood pressure readings will be performed unless manual reading is needed. If systolic blood pressure is >180 mmHg at the 1-hour (± 15 minutes) check, stop the infusion and recheck blood pressure after 15–30 minutes. If blood pressure is not <160 mmHg, recheck blood pressure after another 15–30 minutes. If blood pressure is still not <160 mmHg, the subject is to be discontinued from the trial. The infusion can be resumed in subjects whose blood pressure lowers to <160 mmHg at the first or second recheck. If systolic blood pressure again increases beyond 180 mmHg, the infusion should be stopped and the subject is to be discontinued from the trial. If systolic blood pressure is >180 mmHg at infusion completion, recheck blood pressure after 15–30 minutes. If blood pressure is not <160 mmHg, recheck blood pressure after another 15–30 minutes. If blood pressure is still not <160 mmHg, the subject is to be discontinued from the trial.

Subjects whose treatment is interrupted or permanently discontinued due to an AE including abnormal laboratory value must be followed at least once a week for 4 weeks and subsequently at 4-week intervals until resolution of the event to Grade 1 or better. Dose interruptions should be reported on the appropriate Dosage Administration case report form (CRF). Any AE during Cycle 1 that delays administration of Cycle 2 by more than 7 days will be considered a DLT (see Section 8.0 — Statistical Considerations). The maximum time allowed for toxicity-related treatment interruption for all subsequent cycles is 3 weeks from the intended dosing day. If interruption is > 3 weeks, the subject must be discontinued from the trial treatment. However, the subject will continue to be followed for toxicity.

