histologically confirmed recurrent, locally advanced or metastatic Merkel Cell Carcinoma (MCC) who had not received prior systemic therapy for their advanced disease.

OR

histologically confirmed advanced renal cell carcinoma (RCC) first-line treatment.

OR

histologically confirmed metastatic small cell lung cancer (SCLC) with disease progression on or after platinum-based chemotherapy and at least one other prior line of therapy.

OR

histologically confirmed refractory primary mediastinal large B-cell lymphoma (PMBCL), who have relapsed after two or more prior lines of therapy.

OR

MSI-H or dMMR unresectable or metastatic cancer that has relapsed after prior treatment and has no satisfactory alternative treatment options;

OR

adult patients with unresectable or metastatic tumor mutational burden-high (TMB-H) [≥ 10 mutations/megabase (mut/Mb)] solid tumors;

- Measurable disease based on RECIST 1.1;
- Eastern Cooperative Oncology Group (ECOG) performance status of 0–2 (see Section 11.3);
- Life expectancy ≥ 6 months;
- Adequate organ function as defined in Table 4. All screening labs should be performed within 28 days of treatment initiation.

Table 4

System	Laboratory Value
Hematological	
Absolute neutrophil count (ANC)	$\geq 1,500/\text{mm}^3$
Platelets	$\geq 100,000/\text{mm}^3$
Hemoglobin	≥ 9 g/dL (transfusion permitted)
Renal	
Serum creatinine OR Measured or calculated ^a creatinine clearance (CrCl) (glomerular filtration rate can be used in place of creatinine or CrCl)	≤ 1.5 X upper limit of normal (ULN) OR ≥ 60 mL/min for subject with creatinine levels > 1.5 X institutional ULN
Hepatic	
Serum total bilirubin	≤ 1.5 X ULN OR Direct bilirubin \leq ULN for subjects with total bilirubin levels > 1.5 ULN
ALT and AST	≤ 2.5 X ULN OR ≤ 5 X ULN for subjects with liver metastases
Albumin	≥ 2.5 mg/dL
Coagulation	
International normalized ratio (INR) or prothrombin time (PT)	≤ 1.5 X ULN unless subject is receiving anticoagulant therapy as long as PT or PTT is within therapeutic range of intended use of anticoagulants
Activated partial thromboplastin time (aPTT)	≤ 1.5 X ULN unless subject is receiving anticoagulant therapy as long as PT or PTT is within therapeutic range of intended use of anticoagulants

^a CrCl should be calculated per institutional standard.

- Cardiac ejection fraction of $\geq 45\%$;

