5.1.3 Subject Exclusion Criteria

Subjects meeting any of the following exclusion criteria must be excluded from participating in the trial:

- History of poorly controlled hypertension (defined as systolic blood pressure > 150 mmHg). Subjects with medication-controlled hypertension are allowed provided they have been on their current medication for at least 4 weeks prior to Cycle 1, Day 1;
- History of New York Heart Association class III or greater cardiac disease (see Section 11.4);
- History of myocardial infarction, stroke, ventricular arrhythmia, or symptomatic conduction abnormality within the past 12 months;
- History of congenital QT prolongation;
- Absolute corrected QT interval of > 480 msec in the presence of potassium > 4.0 mEq/L and magnesium > 1.8 mg/dL;
- Currently participating and receiving study therapy or has participated in a study of an investigational agent and received study therapy or used an investigational device within 4 weeks of the first dose of the trial treatment;
- Concurrent use of medications that interact with nitrate/nitrites (see Section 11.5);
- Concurrent use of any complementary or alternative medicines;
- Has a diagnosis of immunodeficiency or is receiving systemic steroid therapy or any other form of immunosuppressive therapy within 7 days prior to the first dose of trial treatment;
- Known history of active tuberculosis (Bacillus Tuberculosis);
- Hypersensitivity to L-NMMA, pembrolizumab, or any of their excipients;
- Has had a prior anticancer monoclonal antibody within 4 weeks prior to study Day 1 or who has not recovered (i.e., \leq Grade 1 or at baseline) from AEs due to agents administered more than 4 weeks earlier;
- Has had prior chemotherapy, targeted small molecule therapy, or radiation therapy within 4 weeks prior to study Day 1 or who has not recovered (i.e., \leq Grade 1 or at baseline) from AEs due to a previously administered agent.

- Note: Subjects with \leq Grade 2 neuropathy are an exception to this criterion and may qualify for the trial.
 - Note: If subject received major surgery, they must have recovered adequately from the toxicity and/or complications from the intervention prior to starting the trial treatment.
- Has a known additional malignancy that is progressing or requires active treatment. Exceptions include basal cell carcinoma of the skin or squamous cell carcinoma of the skin that has undergone potentially curative therapy or in situ cervical cancer.

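### The hepatic rules in 5.2.1.2 ignore baseline: a subject admitted with raised liver values and held for a rise cannot, as written, resume pembrolizumab on return to the entry value

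*Combined protocol and SAP*

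**What the plan says.** **Entry (Section 5.1.2, Table 4).** ALT and AST may be up to 2.5 × ULN, or up to "5 X ULN for subjects with liver metastases". Total bilirubin may be up to 1.5 × ULN. Alternatively, direct bilirubin must be no higher than "ULN for subjects with total bilirubin levels > 1.5 ULN". That second route sets no upper limit on total bilirubin.

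**Hold (Section 5.2.1.2, Pembrolizumab).** Withhold for "AST or ALT > 3 and up to 5 X ULN or total bilirubin > 1.5 and up to 3 X ULN".

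**Permanent discontinuation (same section).** "AST or ALT > 5 X ULN or total bilirubin > 3 X ULN". One sub-item refers to baseline: "For subjects with liver metastasis who begin treatment with Grade 2 ALT or AST", with discontinuation at a rise of 50% or more that persists for a week. It covers ALT/AST only and sits only in the discontinuation list.

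**Resumption (same section).** "Resume pembrolizumab in subjects whose AEs recover to Grade" 0–1. Return to baseline is not offered as an alternative. The exclusion criteria (Section 5.1.3), on recovery from earlier therapy, do offer it: "Grade 1 or at baseline) from AEs due to agents administered more than 4 weeks earlier".

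**Consequences of a delay.** Under 5.2.1.2 and 8.0, an adverse event in Cycle 1 that puts Cycle 2 back by more than 7 days is a DLT. Under 5.2.1.2, a toxicity interruption of more than 3 weeks in a later cycle ends trial treatment. Section 5.6 lists both as reasons to leave the trial.

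**The concern.** Two groups that Table 4 deliberately lets in have entry values inside, or beyond, the ranges at which 5.2.1.2 acts: subjects with liver metastases and ALT/AST above 3 and up to 5 × ULN, and subjects with normal direct bilirubin and total bilirubin above 1.5 × ULN. The thresholds are absolute multiples of ULN and do not say how to treat a value that was there at the start. The resume rule then asks for a grade that these subjects did not have on entry.

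What is at stake is whether a subject whose liver tests rise and then settle back to the starting level may be re-dosed, and whether the wait is recorded as a DLT. The trial plans 12 evaluable subjects in cohorts of 2, and DLTs are the data that drive the dose decisions.

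**Working it through.** There is no planned figure to reproduce. The check passes the Table 4 entry ranges through the rules of 5.2.1.2.

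**Assumption.** Appendix 11.1 links to CTCAE v4.03 but does not print the grade limits. I take Grade 0–1 to end where the hold bands begin: 3 × ULN for ALT/AST and 1.5 × ULN for total bilirubin. For ALT/AST this fits the protocol's own description of some liver-metastasis subjects as starting at Grade 2.

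**Step 1. Unchanged entry values, thresholds taken at face value.**

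| Entry value (× ULN) | Admitted by | Rule met |
|---|---|---|
| ALT/AST 3.0 | liver metastases | none |
| ALT/AST 3.1, 4, 5 | liver metastases | hold |
| Bilirubin 1.6, 2, 3 | normal direct bilirubin | hold |
| Bilirubin 3.1, 4 | normal direct bilirubin | permanent discontinuation |

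The liver-metastasis allowance adds 5 − 2.5 = 2.5 × ULN of range, and the hold band covers 5 − 3 = 2.0 of it. This is width, not a share of subjects. Every total bilirubin admitted by the direct-bilirubin route lies in the hold or the discontinuation range.

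**Step 2. The same rules applied only to worsening.**

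- ALT entry 3.5, rise to 4.5: 4.5/3.5 − 1 = 28.6%. This is below 50% and below 5 × ULN, so it does not meet a discontinuation rule. If judged clinically significant it is an adverse event (Section 7.2) and lies in the hold band. Back at 3.5, it is still above 3 and the resume rule is not met.
- Bilirubin entry 2.0, rise to 2.5: 2.5/2.0 − 1 = 25%. It is held on the same basis. Back at 2.0, it is still above 1.5 and the resume rule is not met.

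**Step 3. Fall below the entry value needed to resume:** 1 − (lower edge of hold band ÷ entry value).

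| | Entry (× ULN) | Fall needed |
|---|---|---|
| ALT/AST | 3.5 | 1 − 3/3.5 = 14.3% |
| | 4.0 | 1 − 3/4 = 25.0% |
| | 5.0 | 1 − 3/5 = 40.0% |
| Bilirubin | 2.0 | 1 − 1.5/2 = 25.0% |
| | 2.5 | 1 − 1.5/2.5 = 40.0% |
| | 3.0 | 1 − 1.5/3 = 50.0% |

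The entries at 5.0 and 3.0 are limiting cases: a subject already at the top of the hold band has no room to worsen within it.

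**Step 4. Where the wait leads.** In the Step 2 examples the rise is below Grade 3 on the stated assumption, so it does not meet the general Grade 3 criterion for a DLT in 8.0. It becomes a DLT only through the delay rule, if Cycle 2 waits more than 7 days for a grade the subject did not have at entry. In later cycles the same wait reaches the 3-week limit and ends trial treatment. Section 5.2.1.2 does not say whether L-NMMA goes ahead while pembrolizumab is held for a liver value, so the Cycle 1 consequence can follow but need not.

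**Step 5. The 50% clause.** If it adds to the 5 × ULN limit, the two rules cross at 5/1.5 = 3.33 × ULN; above that entry value the 5 × ULN limit is reached first. If it replaces that limit, discontinuation moves to 1.5 × baseline: 6.0 from an entry of 4, and 7.5 from an entry of 5. The text does not say which.

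**The case against.** The best defence is intent. The pembrolizumab paragraph opens with adverse events associated with exposure, Section 7.2 sends conditions present at consent to medical history, and the 50% clause presupposes that subjects starting at Grade 2 are dosed. This is persuasive against the stronger reading that a reader might draw from Step 1: that the first pembrolizumab dose, on Day 5 of Cycle 1, would be withheld at an unchanged entry value and the subject lost as non-evaluable under 3.1. No event can be linked to pembrolizumab before it is given. A site can also query the value before Day 1, and Section 1.2.1 enrols up to 20 subjects to obtain 12 evaluable. The documents do not support that consequence.

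A reader might also point to the 12-week line, "Persistent Grade 2 or 3 AEs (excluding endocrinopathies controlled with hormone replacement therapy) that do not recover to Grade" 0–1, as a second route to permanent discontinuation. The 3-week limit normally acts first: a 3-week cycle plus 3 weeks is about 6 weeks after the last dose.

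Three further objections have some force.

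- Section 7.2 requires a clinically significant change, and a 29% rise may not be one. The gap is therefore limited to rises judged significant that fall short of discontinuation.
- A return to baseline could be recorded as a resolved event. But 5.2.1.2 defines recovery by grade, and 5.1.3 shows that the protocol names baseline separately when it means to allow it.
- Grade 0–1 may be a deliberate safety standard, since the follow-up rules also use it. That is a reason to let the clinical team keep a ceiling. It does not explain why a subject judged fit to start at a given value may not restart at it.

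**Conclusion.** The inconsistency between Table 4 and 5.2.1.2 is real for the two subgroups. The hold thresholds and the bilirubin discontinuation threshold have no baseline qualifier. The framing makes it unlikely that unchanged values were meant to trigger them, but the one baseline-relative clause does nothing for bilirubin or for the hold rule. On the more generous worsening-only reading, a held subject who returns to the entry value still does not meet the resume rule. The possible results are a DLT by delay in Cycle 1 and loss of treatment after more than 3 weeks in later cycles.

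The point is minor and cheap to correct. The documents do not say how many subjects fall in either subgroup, and I make no estimate. The percentages rest on the stated grade boundary and on illustrative entry values. The conclusion also depends on the investigator judging the rise clinically significant and, for the DLT, on the whole of Cycle 2 being delayed.

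A reader might infer that on-treatment direct bilirubin must become a new trigger. The documents give no such rule or limit, and the correction does not need one.

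**What to change.** Add to 5.2.1.2, for subjects with liver metastases entering with ALT/AST above 3 × ULN and for subjects admitted on normal direct bilirubin with total bilirubin above 1.5 × ULN:

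1. The hepatic hold criteria and the bilirubin discontinuation criterion apply only to worsening from the baseline value.
2. Recovery means Grade 0–1 or return to baseline.

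Also state whether the 50% clause replaces the 5 × ULN limit for the liver-metastasis subgroup or adds to it. Replacement would allow values up to 7.5 × ULN from an entry of 5.0, so this is a clinical decision and not one for the statistician.

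The cost is a few sentences and clinical sign-off, with no new assessment and no change to the dose-finding model. The downside is re-dosing at a raised but baseline liver value; the clinical team may keep an absolute ceiling to limit it.

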5.4 Rescue Medications & Supportive Care

5.4.1 Supportive Care Guidelines

Subjects should receive appropriate supportive care measures as deemed necessary by the treating investigator.

L-NMMA:

Subjects with medication-controlled hypertension will continue to take their current blood pressure medication. Subjects not currently taking blood pressure medication will be premedicated with the calcium channel blocker amlodipine to control any L-NMMA-mediated transient increase in blood pressure. Amlodipine will be administered as 10 mg orally once daily for 6 days at each cycle. Amlodipine administration will start the day before the first dose of L-NMMA. Amlodipine dose may be adjusted by the treating physician if needed. Amlodipine dose will be held if systolic blood pressure remains below 100 mmHg.

Pembrolizumab:

Suggested supportive care measures for the management of AEs with potential immunologic etiology are outlined below. For each disorder, attempts should be made to rule out other causes

such as metastatic disease or bacterial or viral infection, which might require additional supportive care. The treatment guidelines are intended to be applied when the investigator determines the events to be related to pembrolizumab.

Immune-Mediated Pneumonitis

Pembrolizumab can cause immune-mediated pneumonitis, including fatal cases. Monitor subjects for signs and symptoms of pneumonitis.

≥ **Grade 2 pneumonitis:** Administer corticosteroids at an initial dose of 1 to 2 mg/kg/day prednisone or equivalent followed by a taper.

Immune-Mediated Colitis

Pembrolizumab can cause immune-mediated colitis. Monitor subjects for signs and symptoms of colitis.

≥ **Grade 2 colitis:** Administer corticosteroids at an initial dose of 1 to 2 mg/kg/day prednisone or equivalent followed by a taper.

Immune-Mediated Hepatitis

Pembrolizumab can cause immune-mediated hepatitis. Monitor subjects for changes in liver function.

Grade 2 hepatitis: Administer corticosteroids at an initial dose of 0.5 to 1 mg/kg/day prednisone or equivalent followed by a taper.

≥ **Grade 3 hepatitis:** Administer corticosteroids at an initial dose of 1 to 2 mg/kg/day prednisone or equivalent followed by a taper.

Immune-Mediated Endocrinopathies

Hypophysitis

Pembrolizumab can cause hypophysitis. Monitor for signs and symptoms of hypophysitis (including hypopituitarism and adrenal insufficiency). Administer corticosteroids and hormone replacement as clinically indicated.

Thyroid Disorders

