7.0 TRIAL PROCEDURES

7.1 Trial Procedures

The Trial Flow Chart — Section 6.0 summarizes the trial procedures to be performed at each visit. Individual trial procedures are described in detail below. It may be necessary to perform these procedures at unscheduled time points if deemed clinically necessary by the investigator.

Furthermore, additional evaluations/testing may be deemed necessary by the investigator for reasons related to subject safety. In some cases, such evaluation/testing may be potentially sensitive in nature (e.g., HIV, hepatitis C, etc.) and thus, local regulations may require that additional informed consent be obtained from the subject. In these cases, such evaluations/testing will be performed in accordance with those regulations.

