7.1.2.3 Vital Signs

The investigator or qualified designee will take vital signs at each physical exam. Vital signs should include temperature, pulse, respiratory rate, and blood pressure. Blood pressure will also be monitored during L-NMMA infusions as described in Section 5.2.1.2 – Dose Modification. Weight will also be measured at each physical exam. Height will be measured at screening only.

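### After an L-NMMA infusion is stopped for systolic pressure above 180 mmHg and restarted, no blood pressure reading is required until it ends, so the second-rise stop rule has no scheduled trigger

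*Combined protocol and SAP*

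**What the plan says.** Section 5.2 sets the infusion length: "L-NMMA will be administered as a 2-hour intravenous (IV) infusion", given on Days 1–5 of each cycle. Section 5.2.1.2 fixes the readings: "At each L-NMMA infusion, blood pressure will be measured before infusion, 1 hour" (±15 minutes) after the start, and at completion. If systolic pressure exceeds 180 mmHg at the 1-hour "check, stop the infusion and recheck blood pressure after 15–30 minutes", with a second recheck after the same interval if pressure is not yet below 160 mmHg. Then: "The infusion can be resumed in subjects whose blood pressure lowers to <160 mmHg at the first or second recheck". The next sentence is the second-rise rule: "If systolic blood pressure again increases beyond 180 mmHg, the infusion should be stopped and the subject is to be discontinued from the trial". A reading above 180 mmHg at completion has its own pathway, with up to two rechecks and discontinuation only if pressure stays at or above 160 mmHg.

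Footnote p of the flow chart (Section 6.0) repeats all of this. Section 7.1.2.3 adds no reading of its own: "Blood pressure will also be monitored during L-NMMA infusions as described in Section 5.2.1.2". The blood pressure item in the Section 5.6 discontinuation list covers failure to fall below 160 mmHg after two rechecks. It does not name a second rise.

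**The concern.** A stop rule works only if something is measured while there is still something to stop. Here the required readings cluster in the pause, when the drug is off. They cease when the drug is turned back on, and the next one comes when the infusion has ended.

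The subject concerned has just shown a systolic pressure above 180 mmHg on this drug. A site that follows the schedule exactly could give the rest of the dose without seeing a second rise that the protocol itself treats as grounds for discontinuation. A rise that settles before completion would never be recorded, and the subject could be dosed again on later days.

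The background data in Section 1.1.5 suggest why the off-drug rechecks do not fill the gap. In the renal cell carcinoma study, a 12 mg/kg bolus raised systolic pressure by up to 25 mmHg, and pressure normalised within 5 minutes of stopping. A value below 160 mmHg taken 15–30 minutes after stopping may therefore show mainly that the drug is off, not that re-exposure will be tolerated. Those were boluses in cohorts of three, so they say nothing about how often this would happen with a 2-hour infusion.

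**Working it through.** The plan gives no figure to reproduce here. The check is a timeline.

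**Inputs**
- Infusion length: 120 minutes (Section 5.2).
- Time of the 1-hour check: 60 ± 15, so 45 to 75 minutes after start (Section 5.2.1.2).
- Recheck interval: 15–30 minutes, one or two rechecks (Section 5.2.1.2).
- L-NMMA dose levels: 12.5, 15.0 and 20.0 mg/kg (Section 5.2).
- Assumptions: the infusion resumes at the qualifying recheck, and the remainder is given at the original rate. The documents state no restart rate.

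**Drug off.** One recheck takes 15–30 minutes and two take 30–60 minutes. That gives 1–2 required readings in 15–60 minutes.

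**Drug on after restart.** Time remaining = 120 − time of the 1-hour check.
- Check at 45 minutes: 120 − 45 = 75 minutes remain.
- Check at 60 minutes: 120 − 60 = 60 minutes remain.
- Check at 75 minutes: 120 − 75 = 45 minutes remain.

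Required readings in that period, before completion: 0 in every case. Completion falls between 120 + 15 = 135 and 120 + 60 = 180 minutes after start.

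**Comparison.** In an infusion that never exceeded 180 mmHg, the gap from the 1-hour check to completion is also 45–75 minutes. After restart, the affected subject is on the same schedule as everyone else.

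**Share of dose given without a required reading.** 45/120 = 37.5% to 75/120 = 62.5%.

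| Dose level (mg/kg) | × 0.375 | × 0.625 |
|---|---|---|
| 12.5 | 4.7 | 7.8 |
| 15.0 | 5.6 | 9.4 |
| 20.0 | 7.5 | 12.5 |

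**Alternative reading.** Suppose the 1-hour clock restarted at resumption, which the text does not say. At nominal times the new check would come 60 minutes after restart with 60 minutes of infusion left, so it would coincide with completion. It would fall earlier only if the first check was before 75 minutes and the repeat was early in its window.

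**Effect of adding a reading 15–30 minutes after restart.** Infusion time still to run: 45 − 30 = 15 minutes at the least and 75 − 15 = 60 minutes at the most. That is 15/120 = 12.5% to 60/120 = 50% of the dose.

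**The case against.** The best defence is that the duty to monitor exists and only the interval is missing. Section 5.2.1.2 opens with a general statement that pressure is monitored during infusions and says that readings are automatic. The second-rise rule itself presupposes that someone is watching, and Section 7.1 covers extra checks: "It may be necessary to perform these procedures at unscheduled time points if deemed clinically necessary by the investigator". A sensible clinician would take a reading after restarting. This bears on intent and likely practice, but it does not create a requirement. The general statement carries no interval and is followed at once by the three time points. The automatic-reading sentence describes method, Section 7.1.2.3 points back to the same text, and Section 7.1 leaves the extra check to judgment. A site could comply fully and take none.

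It can also be said that the completion reading is required and would catch a rise that persists. That is true for detection and possible discontinuation, but by then no drug is left to stop.

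Several limits do stand. Over the whole infusion an affected subject has 4–5 required readings against 3 for others, so the lack of closer monitoring applies only to the segment after restart. Section 1.1.5 describes the hypertension seen with L-NMMA as brief and reversible. The risk is further lowered by the exclusion of poorly controlled hypertension (systolic above 150 mmHg, Section 5.1.3), the 160 mmHg restart threshold and Section 5.4.1: "Subjects not currently taking blood pressure medication will be premedicated with the calcium channel blocker amlodipine". The mg/kg figures only restate infusion time multiplied by dose.

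**Conclusion.** The concern holds. Between restart and completion the protocol requires no blood pressure reading, so no required reading can trigger its own second-rise rule while drug is running. Per affected infusion, 45–75 minutes (37.5–62.5% of the dose) is given without a required check, assuming a 120-minute infusion resumed at the original rate. How often this would arise cannot be estimated from the documents, and no harm has been quantified. It is a safety-monitoring gap, with no effect on the sample size, and is best treated as a low-cost improvement. Confidence is high that the timed reading is absent. The clinical consequence is less certain.

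A smaller wording point sits beside it. The text does not say whether a second value above 180 mmHg first seen at completion falls under the second-rise rule or the completion-recheck pathway. The more natural reading confines the second-rise rule to a running infusion, so this needs clarifying but is not a contradiction.

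**What to change.** In Section 5.2.1.2 and footnote p of Section 6.0, require at least one timed automatic blood pressure reading after an infusion is resumed. An interval of 15–30 minutes would match the plan's existing recheck interval. The clinical team should set the final value.

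In the same amendment, state which rule governs a second reading above 180 mmHg first seen at completion (either choice is acceptable), and bring the blood pressure item in Section 5.6 into line.

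The cost is one extra cuff reading per resumed infusion and a short wording change in three places. The one downside is that a subject might be discontinued earlier under a rule the protocol already contains.
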